# Data collection

This pilot RCT will collect both quantitative data and qualitative process evaluation data to inform design considerations for a future full-scale trial.

# **Quantitative Data**

Quantitative data collected from those in the intervention and control groups include measures of mental health and wellbeing (ONS4; sWEMWBS, GAD-7; PHQ-9) and loneliness (UCLA Three-item Loneliness Scale plus an ONS recommended measure). In addition, we will collect data on health service use to inform the health economics evaluation. Outcome measures will be collected at T0 (baseline), T1 (6 weeks after the intervention commences – around 8 weeks post-randomisation) and T2 (post-intervention - around 14 weeks post-randomisation). Full data collection tools are shown in the appendix.

#### ONS4

The ONS4 Personal Wellbeing Scale is a set of four questions developed by the UK Office for National Statistics (ONS) to measure subjective personal wellbeing. It assesses life satisfaction, feelings that life is worthwhile, and happiness, in addition to anxiety. Each of the four questions in the ONS4 Personal Wellbeing Scale is rated on an 11-point 0–10 scale, where 0 is "not at all" and 10 is "completely." There is no total or combined score; instead, each question is analysed separately to assess different aspects of personal wellbeing. For life satisfaction, worthwhile and happiness, higher scores indicate higher levels of personal wellbeing in these areas. In contrast, higher scores on the anxiety question indicate higher levels of anxiety, which can negatively impact upon wellbeing. The questions are shown in Table 1 below and their respective personal wellbeing thresholds in Table 2.

Table 1: ONS4 measures of personal wellbeing

Measure	Question
Life	Overall, how satisfied are you with your life nowadays?
Satisfaction	
Worthwhile	Overall, to what extent do you feel that the things you do in your life are
	worthwhile?
Happiness	Overall, how happy did you feel yesterday?
Anxiety	On a scale where 0 is "not at all anxious" and 10 is "completely anxious", overall,
	how anxious did you feel yesterday?

Source: Office for National Statistics

Table 2: ONS4 Personal wellbeing thresholds

Life satisfaction, worthwhile and happiness			
scores		Anxiety scores	
Response on an 11-point		Response on an 11-point	
scale	Label	scale	Label
0 to 4	Low	0 to 1	Very low
5 to 6	Medium	2 to 3	Low
7 to 8	High	4 to 5	Medium
9 to 10	Very high	6 to 10	High

Source: Office for National Statistics

# **sWEMWBS**

We have obtained the necessary license to use the short Warwick-Edinburgh Mental Wellbeing Scale (sWEMWBS) for this study. The sWEMWBS consists of seven items designed to assess mental wellbeing. Each of the seven statements is rated on a 5-point Likert scale, ranging from 1 (none of the time) to 5 (all of the time). The total score is calculated by summing the individual item scores, resulting in a possible range of 7 to 35, with higher scores indicating better wellbeing (see Table 3). **Error! Reference source not found.** The population mean for the measure is 23.6 (CORQ, Warwick 2011). At the individual level, a 'minimal detectable change' is defined as 1 or 3 points, depending on the analytical method used. This refers to the threshold

at which a change in a person's sWEMWBS score is considered meaningful rather than due to random variation or measurement error.

Table 3: sWEMWBS Items

Questions	Response set
I've been feeling optimistic about the future	
I've been feeling useful	1 None of the time
I've been feeling relaxed	2 Rarely
I've been dealing with problems well	3 Some of the time
I've been thinking clearly	4 Often
I've been feeling close to other people	5 All of the time
I've been able to make up my own mind about things	

#### GAD-7

The Generalised Anxiety Score (GAD-7) asks seven questions, with a Likert scale format (0 to 3), to assess overall levels of anxiety over the previous two weeks and how often specific aspects have been experienced (Table **Error! Reference source not found.**4). The total score is the sum of the individual item scores, with a possible range of 0 to 21. Higher scores indicate greater anxiety: 0 to 4 – minimal anxiety; 5 to 9 – mild anxiety; 10 to 14 – moderate anxiety; 15 to 21 – severe anxiety. If one of the seven items is missing, then the total score is calculated by multiplying the mean of the six non-missing items by 7 and dividing by 6. If two or more items are missing, then the total score is not calculated.

Table 4: GAD-7 scale

Over the last two weeks, how often have you been bothered by the following problems?	Response set
1. Feeling nervous, anxious, or on edge	
2. Not being able to stop or control worrying	0 Not at all
3. Worrying too much about different things	1 Several Days 2 More than half the days
4. Trouble relaxing	3 Nearly every day
5. Being so restless that it is hard to sit still	
6. Becoming easily annoyed or irritable	
7. Feeling afraid, as if something awful might happen	

# PHQ-9

The Patient health Questionnaire (PHQ-9) consists of nine questions, each rated on a Likert scale from 0 to 3, to evaluate the frequency of depressive symptoms over the previous two weeks (see Table 5). **Error! Reference source not found.** The total score is calculated by summing the individual item scores, resulting in a possible range of 0 to 27, with higher scores indicating greater depression severity. The threshold for scores on the PHQ-9 are as follows: 0 to 4 – no depression; 5 to 9 – mild depression; 10 to 14 – moderate depression; 15 to 19 – moderately severe; and 20 to 27 – severe depression. If one item is missing, the total score is estimated by calculating the mean of the eight completed items, multiplying by 9, and dividing by 8. However, if two or more items are missing, the total score cannot be calculated.

Table 55: PHQ-9 scale

Over the last two weeks, how often have you been bothered by the following problems?	Response set
Little interest or pleasure in doing things	
2. Feeling down, depressed or hopeless	0 Not at all
3. Trouble falling asleep, staying asleep, or sleeping too much	1 Several Days 2 More than half the days 3 Nearly every day
4. Feeling tired or having little energy	3 Nearty every day
5. Poor appetite or overeating	
6. Feeling bad about yourself - or that you're a	
failure or have let yourself or your family down	
7. Trouble concentrating on things, such as	
reading the newspaper or watching television	
8. Moving or speaking so slowly that other	
people could have noticed. Or, the opposite -	
being so fidgety or restless that you have been	
moving around a lot more than usual	
9. Thoughts that you would be better off dead or	
of hurting yourself in some way	

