# Missing Data

To minimise missing data, we will use online data collection platforms, including Qualtrics and REDCap. Screening responses to the GAD-7 and PHQ-9 (hosted on Qualtrics) will be mandatory, as these measures are essential for determining participant eligibility. However, at T0, T1, and T2, where responses are optional, participants will be prompted to review their answers to ensure they are satisfied with their responses. If a participant chooses not to answer a question, we will respect their preference and allow them to proceed, as we do not wish to compel responses regarding mental ill health. Missing data will be documented in the pilot study write-up to inform the design of the full-scale RCT. All anonymised data will be securely stored on University of Exeter SharePoint servers in compliance with data protection regulations.

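### The one-missing-item rules for PHQ-9 and GAD-7 divide twice, so prorated totals come out at one-eighth or one-sixth of their proper value

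*Protocol*

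**What the plan says.** The Protocol's PHQ-9 section says the instrument "consists of nine questions, each rated on a Likert scale from 0 to 3". It defines the score plainly: "The total score is calculated by summing the individual item scores, resulting in a possible range of 0 to 27". With one item missing, the rule is to estimate the total by "calculating the mean of the eight completed items, multiplying by 9, and dividing by 8"; and "if two or more items are missing, the total score cannot be calculated".

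The GAD-7 section follows the same pattern: seven items scored 0 to 3, a total that is their sum (0 to 21), no total if two or more items are missing, and, if one is missing, a total obtained by "multiplying the mean of the six non-missing items by 7 and dividing by 6".

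The Missing Data section makes PHQ-9 and GAD-7 responses mandatory at screening. It then continues: "However, at T0, T1, and T2, where responses are optional", participants are prompted to review their answers but may leave a question blank. No other part of the Protocol gives a different proration rule.

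**The concern.** Proration replaces the missing item by the average of the answered ones. It can be written as the mean of the answered items times the full number of items, or as their sum times the full number over the number answered. Both sentences mix these forms: they start from the mean and then also divide by the number answered.

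PHQ-9 and GAD-7 are the Protocol's clinical mental health outcomes and candidates for the definitive trial's primary outcome. The Objectives section asks the pilot for standard deviations to inform that trial's sample size. The Sample size section uses score variability to help choose the primary outcome. The Planned Data Analysis section compares arms adjusted for the baseline score.

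Coded literally, a form with one blank becomes a near-zero outlier, either as an outcome or, at T0, as the covariate. A range check would not catch it, because the wrong value still lies inside 0 to 27 or 0 to 21.

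**Working it through.** **Inputs from the Protocol.** PHQ-9: k = 9 items scored 0 to 3, total 0 to 27. GAD-7: k = 7 items scored 0 to 3, total 0 to 21. With one item missing, m = k − 1 items are answered (8 or 6). S is the sum of the answered items.

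**Formulas.**
- Rule as written: (S/m) × k / m
- Proper proration: (S/m) × k, which equals S × k/m
- Ratio of the first to the second: 1/m, that is 1/8 for PHQ-9 and 1/6 for GAD-7. When S = 0 both give 0.

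**Can the rule reproduce the stated range?** Set every answered item to 3.
- PHQ-9 as written: 3 × 9/8 = 3.375. Proper: 3 × 9 = 27, the stated maximum.
- GAD-7 as written: 3 × 7/6 = 3.5. Proper: 3 × 7 = 21, the stated maximum.

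The rule as written fails this check and the proper form passes it. Both as-written maxima lie below 5, so every prorated form lands in the Protocol's 0 to 4 band (no depression, or minimal anxiety).

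**Typical values.**

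| Instrument | S | As written | Proper |
|---|---|---|---|
| PHQ-9 | 12 | (12/8) × 9/8 = 1.69 | (12/8) × 9 = 13.5 |
| PHQ-9 | 16 | (16/8) × 9/8 = 2.25 | (16/8) × 9 = 18 |
| GAD-7 | 10 | (10/6) × 7/6 = 1.94 | (10/6) × 7 = 11.67 |
| GAD-7 | 12 | (12/6) × 7/6 = 2.33 | (12/6) × 7 = 14 |

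**Effect on the PHQ-9 mean and variance (illustration).** The Protocol gives no item-missingness rate and no expected SD. Assume a mean of 10, an SD of 5, and a fraction p of forms with exactly one blank, unrelated to severity. Those forms then score one-eighth of their proper value.
- Fall in mean: p × 10 × 7/8. At p = 5% this is 0.44.
- New variance: (1 − p) × 25 + p × 25/64 + p(1 − p) × 8.75², where 8.75 = 10 × 7/8.
- At p = 5%: 23.75 + 0.02 + 3.64 = 27.41, a ratio to 25 of 1.10.
- At p = 3%: 24.25 + 0.01 + 2.23 = 26.49, ratio 1.06.
- At p = 10%: 22.50 + 0.04 + 6.89 = 29.43, ratio 1.18.

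Simulating the same set-up with scores clipped to 0 to 27 gives ratios of 1.06, 1.10 and 1.19 for 3%, 5% and 10%. At 1% the ratio is 1.02.

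**Effect on an arm difference.** If p is the same in both arms, the raw PHQ-9 difference shrinks by the fraction p × 7/8, which is 4.4% at p = 5%.

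**The case against.** The arithmetic is hard to dispute; the case on the other side is about consequence.

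- **The main results are untouched.** The primary objective is recruitment and retention. Eligibility is safe because screening items are mandatory. The Planned Data Analysis section says effectiveness is not a key objective and plans no hypothesis tests. All of this stands: the exposure is confined to secondary estimates. The rule also leaves completeness unaffected, since it does not change which forms can be scored.
- **It is a visible slip and reversible.** A programmer may notice a rule that caps at about 3.4 on a 27-point scale, the SAP has still to be signed off before data lock, and totals can be recomputed from item responses. This also stands, but it relies on someone departing from the Protocol's explicit instruction. The SAP is not available here, so whether it corrects the rule is unknown.
- **The number of affected forms is unknown.** Of 84 participants, 5% is about four forms per time point, and the true count could be zero. The percentages above are therefore illustrations only.
- **The knock-on to the definitive sample size is conditional.** It rises in proportion to the variance only if PHQ-9 is chosen as primary outcome, the target difference is fixed in raw points, and the unadjusted SD is carried forward uncleaned. A baseline-adjusted residual SD or an intraclass correlation need not move in the same proportion.
- **Bias in arm differences is small if missingness is balanced.** A larger bias needs different missingness between arms, for which the Protocol offers no evidence either way.

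These points limit the damage. None of them makes either sentence correct.

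**Conclusion.** The concern holds. Both scoring rules are wrong as written and conflict with the score ranges in the same sections. The per-form error needs no assumption: any non-zero prorated total is one-eighth (PHQ-9) or one-sixth (GAD-7) of its proper value, with ceilings of 3.375 and 3.5.

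The aggregate effect does depend on assumptions. With a PHQ-9 mean of 10, an SD of 5 and 3% to 10% of forms missing one item, the variance is inflated by about 6% to 19%. It applies only to T0, T1 and T2 forms with exactly one blank, and only if the rule is coded literally. It should be corrected before the SAP is signed off, because it bears on the SDs and adjusted differences the pilot is meant to supply.

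**What to change.** In the PHQ-9 section, state that with one item missing the total is the mean of the eight completed items multiplied by 9 (equivalently, their sum multiplied by 9/8). In the GAD-7 section, state that it is the mean of the six completed items multiplied by 7 (equivalently, their sum multiplied by 7/6). Use the same wording in the SAP and the scoring code. Add a code check that a form with one blank and every other item at 3 scores 27 or 21.

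The cost is two sentences. Nothing changes in data collection, and any totals already derived can be recalculated from the item responses.

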#### Loneliness

The ONS recommends four items to measure loneliness; three indirect questions that comprise the UCLA Three-Item Loneliness scale (which are summed to give an overall score) and a separate direct question about how often the respondent feels lonely (Table 6).

The UCLA Three-Item Loneliness Scale consists of three questions assessing different aspects of social isolation and perceived loneliness. Each item is scored on a three-point Likert scale, with responses ranging from "Hardly ever or never" (1) to "Often" (3). The total score is obtained by summing the responses to the three items, with higher scores indicating greater loneliness.

The single-item direct measure, asking "How often do you feel lonely?". This question is rated on a five-point scale, ranging from "Never" (1) to "Often/Always" (5), with higher scores indicating greater loneliness.

The ONS does not specify cut-off scores to categorise loneliness levels. Instead, scores are typically analysed as continuous variables, where lower scores suggest fewer feelings of loneliness, and higher scores indicate greater loneliness.

Table 6: Loneliness Measures

Measures	Items	Response categories
The UCLA Three-Item Loneliness scale	1. How often do you feel that you lack companionship?	
	2. How often do you feel left out?	1 Hardly ever or never 2 Some of the time
	3. How often do you feel isolated from others?	- 3 Often

The direct measure of	How often do you feel lonely?	5 Often/always,
loneliness		4 Some of the time,
		3 Occasionally,
		2 Hardly ever,
		1 Never

Source: Office for National Statistics

(https://www.ons.gov.uk/peoplepopulationandcommunity/wellbeing/methodologies/measuringlonelinessguidanceforuseofthenationalindicatorsonsurveys)

#### **Decliner Data**

Decliner questionnaires will be sent to those who are eligible to participate but choose not to and drop out. The questionnaire will be sent to those who do not complete the 6 sessions (see appendix).

#### Cost Data

Cost data will be collected from the nature-based partners to understand the full cost of delivering the intervention, and a health service use questionnaire will be completed by participants to establish usual care and assess the impact on usual care of the nature-based intervention.

# **Qualitative Data**

The qualitative component of this pilot RCT will be a process evaluation designed to assess the acceptability of the intervention and trial procedures. This evaluation will provide valuable insights into participant experiences of the trial processes and the practical implementation of the intervention. Findings will inform refinements to the study design and delivery ahead of a future definitive RCT, ensuring that it is both methodologically robust and practically viable.

To achieve this, qualitative data will be collected through:

#### 1. Participant Focus Groups (Intervention Group)

One focus group discussion will be conducted at each intervention site, with participants purposively sampled to ensure diversity in personal characteristics (e.g., age, gender, work status). Thus, there will be three participant focus groups in total. These discussions will explore participants' experiences of the intervention, elucidating potential barriers to engagement and suggestions for improvement. Additionally, participants will reflect on the research process itself, including recruitment, consent, data collection, and any perceived burden of participation. Understanding these factors will help refine both the intervention and trial procedures to enhance participant retention and engagement in the future definitive RCT.

#### 2. Waitlist Control Group Focus Group

A separate focus group will be conducted with participants allocated to the waitlist control group to explore their experiences of delayed participation. This will assess

whether the waitlist control design influences participant motivation, engagement, or expectations of the intervention. Additionally, it will explore whether participants allocated to the waitlist control group engaged in any nature-based activities prior to their engagement in the intervention. Insights from this group will help determine whether a waitlist control remains a suitable comparator for the full RCT or if modifications are needed to improve adherence and retention.

#### 3. Nature-Based Provider Focus Group

A focus group will be conducted with facilitators and providers delivering the intervention to explore their experiences of engaging with the research project. Discussions will identify factors that support or challenge their involvement, including logistical, practical, and resource-related considerations. This will ensure that delivery of the intervention is feasible and sustainable for providers, helping to refine intervention delivery before scaling up. This will be complemented by ongoing provider engagement meetings and record keeping. Regular contact meetings with nature-based providers will be held throughout the trial to maintain engagement, identify ongoing challenges, and document potential solutions in real-time. These meetings will help address emerging implementation issues, ensuring that facilitators feel supported, and that intervention fidelity is maintained. Capturing provider perspectives on an ongoing basis will provide valuable considerations for the scalability of the intervention model for the future RCT.

# **Assessment Processes**

Table 7: Quantitative data collection

Tool	Purpose	How*	When
Decliner survey	To understand non-	Self-reported online	At recruitment
	participation	survey – including	
		free text space	
Screening PHQ9	To ensure	Self-reported online	Prior to consent
and GAD7	participants meet	screening tool with	
	inclusion criteria	associated support signposting	
Participant	To describe study	Self-report online	After consent, baseline
characteristics	demographics &	questionnaires	questionnaire T0
	any current MH		
	treatment		
Mental health:	Clinical MH	Self-report online	After consent baseline
PHQ9	outcome measures	questionnaires	questionnaire (T0),
GAD7			post-intervention follow-
			up (T1), follow-up (T2)
Wellbeing:	Clinical wellbeing	Self-report online	After consent baseline
ONS4	measures	questionnaires	questionnaire T0,
SWEMWEBS			Post randomisation T1,
			follow up T2

Loneliness: UCLA (3 item scale) Direct questions	To describe level of loneliness	Self-report online questionnaire	After consent baseline questionnaire T0, Post randomisation T1, follow up T2
Health economics	Healthcare use questionnaire	Self-report online questionnaires	After consent baseline questionnaire T0, Post randomisation T1, follow up T2
Participation survey	Understanding processes and issues, extent of nature-based activity by control group during their wait period, and including group dynamics that may be hard to establish in the focus group	Self-reported online survey – including free text space	Post-intervention (T1)
Drop Out/Withdrawer Survey	Understanding reasons for withdrawing from the research, relevant to both active intervention groups and waitlist controls	Self-reported online survey – including free text space	Any time post- randomisation

\* For online questionnaires, all participants will be offered the option of research support over the phone or zoom/teams call to support completion where required.

Table 8: Qualitative data collection

Purpose	Who	How	When
To understand how	Nature-based	Research	During the
planned activities	providers and	observation	intervention
are mapped to	participants		
handbook			
mechanisms			
To understand	Participations in the	Focus group	Post-intervention
participants'	intervention arm	discussions (one at	
experiences of trial		each of the three	
processes (including		sites)	
randomisation,			
questionnaires etc)			
To understand	Participations in the	Focus group	Prior to their
participants'	control arm	discussions	participation in the
experiences of trial			wait list intervention.
processes (including			
randomisation,			

communication, wait list control, type of nature-based activity during their wait period etc.)			
To understand the experience of trial participation (support, challenges, payments etc)	Nature-based providers	Focus group discussions	After the wait list intervention has taken place.

# **Trial Procedures**

Participation in the trial will involve:

- Written consent
- Completion of the screening tool
- Completion of the baseline questionnaires (T0) for both the intervention and control arms:
  - Participant characteristics
  - o Mental health and wellbeing measures
  - o Health service use questionnaire
- Random allocation to either the intervention arm (nature-based activities) or the control arm (usual care, wait list)
- Those allocated to the intervention arm will participate in a 6-week programme of nature-based activities. An initial optional induction session prior to the first group session will also be available.
- Completion of questionnaires after the intervention at T1 (8 weeks post-randomisation) and T2 (14 weeks post-randomisation) arm:
  - Mental health and wellbeing measures
  - o Loneliness measure
  - Health service use questionnaire
- Participation in a focus group discussion about their experience of the processes and delivery of pilot trial (optional) following T2
- Completion of T1 and T2 questionnaires for the waitlist control group:
  - Mental health and wellbeing measures
  - Loneliness measure
  - Health service use questionnaire
- Those allocated to the control arm will be offered the opportunity to take part in a 6-week programme of nature-based activities after the follow-up period (T2).

